STUDY PROTOCOL AND STATISTICAL ANALYSIS PLAN

Using a randomized control trial to evaluate the effectiveness of glove changing in reducing wound-related complications following cesarean section in Vietnam

Principle investigator	[name] Obstetrician – Gynecologist Hung Vuong hospital Ho Chi Minh city, Vietnam
Protocol identification number	CK62721303 (dated September 14, 2020)

Abbreviations

CS	Cesarean section
SSI	Surgical site infection
CPR	Cardiopulmonary resuscitation
ASA	American Society of Anesthesiologists
NYHA	New York Heart Association

Table of contents

1. Introduction 4

2. Study design 4

3. Aims and objectives 6

4. Outcomes 6

5. Populations and subgroups to be analyzed 6

6. Analyses 6

7. References 6

1. Introduction

[figure not shown]
The aim of this study is to investigate the effect of glove changing on wound complications after cesarean surgery in Vietnam. We hypothesize that changing gloves prior to abdominal closure reduces the incidence of infectious complications following cesarean surgery.

2. Study design

Study subjects will be recruited from December 2020 to February 2021 at Hung Vuong hospital, Ho Chi Minh city, Vietnam. Inclusion criteria for participants in this study include pregnant women who are 18 years old or higher; who have CS performed at Hung Vuong hospital; and who live close to Ho Chi Minh city and agree to return for postpartum care one-month post-surgery. Exclusion criteria include pregnant women who have fever during labor; who have systemic infectious conditions; who have surgical site infection SSI or sexually infectious conditions; who have ongoing internal conditions such as pre-eclampsia, severe anemia, American Society of Anesthesiologists (ASA) ≥ 3 , New York Heart Association (NYHA) class 3 or above, pulmonary edema, or severe asthma. Data collection will be stopped when pregnant women require cardiopulmonary resuscitation (CPR) or have damaged pelvic organs during CS; when they need extra surgery after CS; or when the surgical team has double gloving or the gloves get punctured during surgery.

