The study is a parallel-group randomized control trial with 2 arms. Arm 1 includes patients who will have glove changed prior to abdominal closure during CS. Arm 2 includes patients who will not have glove changed prior to abdominal closure during CS. All patients are randomized using computer-generated sequences with allocation ratio 1:1. Clinic visits are performed at 2 time points, unless emergency check-up is recommended after hospital discharge. Visit 1 is at 2-3 days post-surgery and visit 2 is at 30 ± 2 days post-surgery where primary and secondary outcomes are measured. The study is concluded when we finish the second data collection or when patients are discharged from the hospital after a required immediate check-up. Patients who do not return for postpartum care will be considered lost to follow up. The study design is visualized in Figure 1 below.

Figure 1: The CONSORT flow diagram of the study

Sample size calculation

The sample size is calculated based on the following formula:

$$n = \frac{\left(Z_{1-\frac{\alpha}{2}}\sqrt{2P(1-P)} + Z_{1-\beta}\sqrt{P_1(1-P_1) + P_2(1-P_2)} \right)^2}{(P_1 - P_2)^2}$$

Where:

n: required minimum sample size in each group

P1: rate of superficial SSI in group 1 (i.e., glove change group)

P2: rate of superficial SSI in group 2 (i.e., control, or usual care group)

$$P = \frac{P_1 + P_2}{2}$$

α : type I error, $\alpha = 0,05 \rightarrow Z_{1-\alpha/2} = 1,96$

β : type II error, $\beta = 0,15$ (statistical power = 0,85) $\rightarrow Z_{1-\beta} = 1,04$

Based on the results from Scrafford's group where they reported the rates of superficial SSI in the glove change group and the usual care group were 6.4% and 13.6%, respectively [1], we will calculate the sample size for each group. In order to achieve the statistical power of 0.85, the required minimum sample size in each group is 310. To account for 5% of the sample lost

during the study, the sample size in each group is increased to 327 based on the calculation $310/0.95=327$. Thus, the required minimum sample size for both groups in our study will be $327*2=654$.

3. Aims and objectives

The aims are 1) to evaluate whether changing gloves during CS reduces complications and SSI, and 2) to identify other factors that are associated with complications and SSI.

4. Outcomes

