The primary outcomes of interest are any wound complications occurring after the surgery, including seroma, hematoma, wound separation, and wound infection. Secondary outcomes are any signs of SSI, including fever, swelling, redness, and pain surrounding the incisional area. The outcomes will be evaluated during clinic visits by qualified medical practitioners who are blind to the intervention group assignment.

5. Populations and subgroups to be analyzed

Populations: intention-to-treat

Subgroups: the glove change and usual care group. These 2 subgroups will be analyzed using intention-to-treat populations.

6. Analyses

Data will be analyzed using Stata 16 (StataCorp LLC, College Station, TX). Normally distributed data will be expressed as mean \pm standard deviation, while non-normally distributed data will be shown as medians with interquartile ranges. T-test for normally distributed continuous variables and Mann-Whitney-U test for non-normally distributed continuous variables will be used to compare between groups. Categorical variables will be reported as absolute numbers and percentages; the Chi-square test or Fisher's exact test will be utilized for comparison. A p -value of <0.05 will be considered statistically significant. Multiple logistics regression analysis will be performed to identify factors affecting the superficial incisional complications.

7. References

[1] J. D. Scrafford, B. Reddy, C. Rivard, and R. I. Vogel, "Effect of intra-operative glove changing during cesarean section on post-operative complications: a randomized controlled trial," *Arch Gynecol Obstet*, vol. 297, no. 6, pp. 1449–1454, Jun. 2018, doi: 10.1007/s00404-018-4748-y.

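### The 85% power and 310 per group are derived for superficial SSI, not for the stated primary outcome of any wound complication

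*Combined protocol and SAP*

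**What the plan says.** The sample size calculation in section 2 defines its control and intervention rates as superficial SSI rates: "P1: rate of superficial SSI in group 1 (i.e., glove change group", with the matching definition for usual care. It takes the values from one earlier trial, which it says "reported the rates of superficial SSI in the glove change group and the usual care group were 6.4% and 13.6%, respectively". From these it concludes: "In order to achieve the statistical power of 0.85, the required minimum sample size in each group is 310". Allowing for 5% loss gives 327 per group and 654 in total.

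Section 4 names a different endpoint: "The primary outcomes of interest are any wound complications occurring after the surgery, including seroma, hematoma, wound separation, and wound infection". Signs of SSI are secondary. Superficial SSI is not listed there as an outcome; the nearest item is wound infection, one of the four named components.

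The naming varies elsewhere. The Introduction gives the aim as "The aim of this study is to investigate the effect of glove changing on wound complications after cesarean surgery in Vietnam", but its hypothesis is that "changing gloves prior to abdominal closure reduces the incidence of infectious complications following cesarean surgery". The first aim in section 3 is "to evaluate whether changing gloves during CS reduces complications and SSI", which treats complications and SSI as two things. Section 6 sets one threshold for all tests: a p-"value of <0.05 will be considered statistically significant".

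**The concern.** A power statement belongs to the endpoint whose rates went into it. Here those rates are labelled superficial SSI, while the primary comparison is on any wound complication. The two overlap through wound infection but are not the same. The plan gives neither the frequency of the other three components nor the effect expected on them.

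The 310 per group is the plan's only justification of the trial's size. If it does not carry over to the primary outcome, the plan does not say what effect on that outcome the trial could detect. A non-significant primary result would then have no planned sensitivity to be read against. The plural in section 4 also leaves open whether there is one composite or four separate primary outcomes.

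**Working it through.** **Inputs.** From section 2: P1 = 0.064, P2 = 0.136, two-sided α = 0.05 (z = 1.96), power 0.85 (z = 1.04), 1:1 allocation, 5% loss. For any wound complication the documents give no rate, so every composite rate below is an assumption.

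**Reproducing the plan's figure.** With P = (0.064 + 0.136)/2 = 0.10:

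- √[2P(1−P)] = √0.18 = 0.4243
- √[P1(1−P1) + P2(1−P2)] = √(0.0599 + 0.1175) = 0.4212
- n = (1.96 × 0.4243 + 1.04 × 0.4212)² / 0.072² = 310.9, or 310.2 with the unrounded z of 1.0364
- 310/0.95 = 326.3, hence 327 per group and 654 in total

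The stated figures reproduce for superficial SSI. Strict rounding up would give 311, which is immaterial.

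**Power for a composite at 310 per group.** The same formula solved for power is

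power = Φ{ [(P2 − P1)√n − 1.96√(2P(1−P))] / √[P1(1−P1) + P2(1−P2)] }.

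*(1) Added events unaffected by gloves.* Add c to both rates for women who have a complication but no superficial SSI:

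| c (assumed) | Glove arm | Control arm | Power |
|---|---|---|---|
| 0 | 6.4% | 13.6% | 0.850 |
| 2 points | 8.4% | 15.6% | 0.789 |
| 5 points | 11.4% | 18.6% | 0.710 |
| 10 points | 16.4% | 23.6% | 0.611 |

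For c = 5 points: (0.072 × √310 − 1.96 × 0.5050)/0.5024 = 0.553, and Φ(0.553) = 0.710.

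*(2) Same relative effect on the whole composite.* The risk ratio is 0.064/0.136 = 0.47:

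| Control rate (assumed) | Power |
|---|---|
| 10% | 0.715 |
| 13.6% | 0.850 |
| 15% | 0.886 |
| 18.6% | 0.948 |

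The 10% row requires a local rate below the cited 13.6%; it does not follow from the endpoint mismatch alone.

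*(3) Break-even.* Let gloves multiply the added events by r, so the rates are 0.064 + c·r and 0.136 + c. Power stays at 0.85 when r = 0.737, 0.755 or 0.780 for c = 2, 5 or 10 points. That is a cut in the added events of about 26%, 25% or 22%. A larger cut puts power above 85%, a smaller one below.

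*(4) Detectable difference.* At 85% power and 310 per group:

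| Control rate (assumed) | Glove arm | Difference |
|---|---|---|
| 15.0% | 7.4% | 7.6 points |
| 18.6% | 10.2% | 8.4 points |
| 23.6% | 14.2% | 9.4 points |

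*(5) If four separate primary outcomes are meant.* The 85% then covers at most wound infection, tested at an unadjusted 0.05. With an even split (assumed), α = 0.05/4 = 0.0125, power for 6.4% against 13.6% is 0.689, and 85% would need 432 per group.

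**The case against.** The strongest reply is that this may be a labelling slip. The plan uses its outcome terms loosely, and superficial SSI is not an outcome in section 4. If 6.4% and 13.6% are in fact composite rates, both the 310 and the 85% stand. That possibility is real, and the documents alone cannot settle it. But the text calls them superficial SSI in both rate definitions and again in the sentence citing them, so as written the mismatch stands.

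It can also be said that sizing on an overlapping component with a published effect is a common pragmatic choice. A broader composite brings more events, and the break-even reductions of about 22% to 26% are roughly half the 53% assumed for SSI (1 − 0.47). All of this is fair, and it rules out calling the trial underpowered. It does not supply the missing support, because the plan nowhere states an effect on seroma, hematoma or wound separation, and its hypothesis speaks only of infectious complications.

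Two further points stand in part. The section 4 wording reads most naturally as one composite, so the four-outcome figures are conditional and secondary. Observed rates would also help in reading a null result; what is missing is the planned sensitivity.

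**Conclusion.** The concern holds. As written, the plan's only power statement belongs to an endpoint that section 4 does not list, and nothing elsewhere supplies a rate, effect or power for the primary outcome. The 85% is unsupported for the primary comparison; it is not shown to be too high.

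The direction depends on assumptions the plan does not make. At 310 per group, power runs from about 0.61 (10 added points, no glove effect on them) to about 0.95 (risk ratio 0.47 throughout, control rate 18.6%). This conclusion takes the plan's own label for the two rates at face value. It should be corrected, but it does not invalidate the trial.

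**What to change.** 1. Check in the cited source which endpoint 6.4% and 13.6% describe.
2. If they are composite wound-complication rates, correct the definitions of P1 and P2 and the sentence citing the rates. The sample size is unchanged.
3. If they are superficial SSI rates, state that the 85% applies to superficial SSI only. Then give the power of 310 per group for the primary outcome under stated assumed composite rates, or a detectable-difference statement such as 18.6% against 10.2%.
4. State whether the primary outcome is one composite or four separate outcomes.
5. Use one endpoint name in the hypothesis, the sample size calculation and section 4.

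The cost is one source check, some rewording and one added figure. No extra patients are needed and the primary outcome can stay as it is. The stated power may turn out less favourable than 85%, and the sponsor would have to accept that.
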